2. STUDY SUMMARY

Health care personnel (HCP) frequently receive annual influenza vaccinations and a substantive proportion of them might have attenuated or no response to additional standard dose influenza vaccines. In this population that is seasonally exposed to influenza illnesses and repeatedly vaccinated using standard dose (SD) vaccines, adjuvanted (AD) vaccines might elicit a better immunity than the typically used SD. We therefore propose to conduct a double-blinded randomized controlled vaccine trial among HCPs to determine if AD influenza vaccines generate superior seroprotection against influenza than SD vaccines particularly among previous sub-optimal responders.

The trial will be conducted at two hospital sites in Lima-Peru during the 2022 influenza season. It has annual circulation int the country, but with increases during the months of June to October, which coincides with winter. The study is aimed to HCP who were enrolled in the Cohort study of Influenza and other Respiratory Viruses among HCP in Peru (approximately 1500). The number of participants to be enrolled is 800 approximately. The study design is a randomized, double-blind vaccine trial. Eligible HCP at each site who consent to participate will be randomized 1:1 to receive either a single dose of AD (FLUAD, quadrivalent, Seqirus) or SD (VaxigripTetra, quadrivalent, Sanofi-Pasteur). Participants, researchers and laboratory staff performing the assays will be blinded to the vaccine information.

Participants will be invited to attend the study site for a study screening and assessment of eligibility criteria, if they agree to participate and once consent form is signed, they will visit the site at day 0 for vaccination and medical assessment. Another brief medical adverse event assessment will be performed on days 3 and 7. Participants will be also prompted to begin active surveillance for acute illnesses as soon as US Center of Prevention and Control of Disease (US CDC) and the study site PI confirm that seasonal influenza is circulating locally or there are indicators that circulation is imminent. During the influenza season, participants will be followed up twice a week via SMS or phone calls to assess if they become sick with a respiratory event, if so, they will be asked questions about their illness through an acute illness survey and a swab sample will be requested.

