7. OBJECTIVE

Primary objective:

-To determine if AD influenza vaccine generates superior immunogenicity than the non-adjuvanted SD influenza vaccine, at approximately 28 days after vaccination and at the end of season, among HCP

Secondary objectives:

-To compare immune responses post-vaccination, at approximately 28 days after vaccination and at the end of season, among HCP with a history of PCR-confirmed influenza infection during any of the six cohort years (2016 to 2021)

-To compare immune responses post-vaccination, at approximately 28 days after vaccination and at the end of season, among HCP with no history of PCR-confirmed influenza infection during the six cohort years (2016 to 2021), among those with data available for the six cohort years -To examine whether the number of prior influenza vaccination during the preceding 10 years, as documented by medical records, modifies immune responses after receipt of vaccination with AD or SD influenza vaccine, at approximately 28 days after vaccination and at the end of season -To evaluate laboratory-confirmed influenza illness rates in the group receiving AD influenza vaccination compared to the group receiving SD influenza vaccination

-To analyze and identify risk factors for sub-optimal response (lack of seroconversion/seroprotection) to SD and/or AD influenza vaccines

- To assess the adverse events among HCP receiving SD and AD influenza vaccines

the studies in reference are those entitled: "Effectiveness of influenza vaccine to prevent infection by influenza virus, loss of hours of work and patient exposure: A prospective cohort study in health workers " that was carried out during the years 2016 to 2019 and "Effectiveness of the influenza vaccine to prevent infection by the influenza virus, loss of working hours and patient exposure: A prospective cohort study in health workers in the context of the COVID-19 pandemic "that was carried out between 2020-2021. Both studies were observational epidemiological studies in hospitals in Lima .

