10.1 Study population

Eligible adult participants (age 18 or older) will work in one of the selected healthcare facilities (Cayetano Heredia National Hospital, and Arzobispo Loayza National Hospital) and will meet the following inclusion criteria:

Inclusion criteria:

- Be aged ≥18 years old;
- Have participated in the healthcare personnel cohort study between 2016 and 2021.
- Work at the facility full-time (≥30 hours per week);
- Have routine, direct, hands-on or face-to-face contact with patients (within 1 meter) as part of a typical work shift, including, but not limited to, physicians, nurses, respiratory therapists, physical therapists, unit clerks, radiograph technicians, medical assistants, and transporters;

- Work at the facility for ≥1 year prior to enrollment and planning to continue working at the facility for one year after enrollment;

- Willing to receive influenza vaccination (either AD/SD)

-Women of childebaring age have to complete the following criteria:

- Negative urine pregnancy test performed by the study staff within 24 hours preceding receipt of vaccination
- Willing to use use another reliable form of contraception approved by the Investigator that they select to use for at least 2 months after receiving the vaccine. If they are not using, we will provide access to contraceptives.
- Do not be in breastfeeding period

Exclusion criteria:

- Be vaccinated against influenza in the current season (influenza season 2022)
- Have severe, life-threatening allergies against influenza vaccines, eggs or influenza vaccine components
- Have a history of Guillain-Barré Syndrome or other autoimmune diseases
- Received blood or blood products within 3 months before enrollment
- Be pregnant, confirmed by rapid pregnancy test

The participation from each subject will be from the enrollment (March approximately) until the end of the influenza season

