10.4 Screening/Enrollment Procedures

Enrollment will begin. during influenza season in Peru[23].

Potential volunteers will come to the study clinic for a screening visit at which time they will be invited to sign a written informed consent form. (Appendix C). Prior to any study procedure the investigator or the health care provider designated, will provide each volunteer sufficient time to read the informed consent document and will fully inform the subject of the nature and scope of the study, potential risks and benefits of participation, the study procedures involved, and will answer all questions for the subject prior to requesting the subject's signature on the informed consent form (ICF). A signed ICF will be obtained prior to performing any study-related procedures.

Once the ICF signature has been obtained, the following screening procedures and assessments will be performed and results recorded on the CRF:

- Assignation of screening number
- Inclusion and exclusion criteria review (Appendix B)

- Demographic documentation including including age, sex, race, ethnic origin, height, and weight. Medical documentation: medical history and nature of contact with patient (Appendix E)
- A complete physical examination including head, eyes, ears, nose, and throat (HEENT), heart, lungs, abdomen, skin, lymph nodes, neurological, musculoskeletal systems
- Vital signs including heart rate(HR), blood pressure (BP), respiratory rate (RR), and oral temperature
- All women will have a reproductive status assessment and women with child bearing potential will
 have a urine pregnancy test. It will be performed considering a period of 5 weeks after the last
 menstrual period. Women of reproductive status will be asked about the type of contraception she
 currently uses. If she is not using any form of secure contraception, she will be offered to attend an
 appointment in the family planning program from each hospital. As part of that program she will be
 offer to choose oral or injectable contraception, free of charge, or an alternative secure contraception
 that could be applied in a family planning clinic (like and intra-uterine device). If the family planning
 clinic for any reason does not have the method in stock (oral, injectable or barrier), the study will
 provide it. She can return to be re-screened for the trial once appropriate contraception use has been
 demonstrated and/or documented. She may be re-cheduled in the range of 1 to 4 weeks after the

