10.7 Follow up

Study staff will contact participants on day 3 (Appendix H) and day 7 (Appendix I) to ask about potential adverse effects or reactions participants might have developed after vaccination.

On day 28 (range 21-35 days), participants will provide another 10 ml sample of whole blood (*post-vaccination specimen*, Appendix F).

At the end of the influenza season, participants will provide a final sample of whole blood (10 ml) (*end of season specimen*, Appendix F) and complete an end of season questionnaire (Appendix J).

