10.13 Study outcomes

The primary outcome to be measured will be seroconversion at day 28 after vaccination. Seroconversion will be defined as having a haemagglutination inhibition (HI) geometric mean titre (GMT) of \geq 1:40 in the case the pre-vaccination HI GMT <1:10 or having a four-fold rise in titre in the case the pre-vaccination HI GMT \geq 1:10. We will also measure HI GMT at the end of season. Seroprotection will be defined as having an HI GMT \geq 1:40.

Other outcomes that will be measured include:

-reactogenicity to vaccination

-acceptability of AD influenza vaccination

-acute respiratory illness (ARI)

-ARI-associated outcomes (absenteeism, medical visits, hospitalization, other)

-laboratory-confirmed influenza and other respiratory pathogens

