11. ANALYSIS

11.1 Data analysis

Baseline data will be described and analyzed for group comparison, as a check on the adequacy of randomization procedures. Table 3 includes the dependent variables for the primary objective and the first 4 secondary objectives, including the evaluation criteria for each one (Table 3), while tables 4 and 5 detail the dependent variables for secondary objectives 5 and 6, accordingly.

Primary objective: To determine if AD influenza vaccine generates superior immunogenicity than the nonadjuvanted SD influenza vaccine, at approximately 28 days after vaccination and at the end of season, among HCP.

				Criterios de	Tipo de	Instrumento de
	Dimensión	Indicador	Valores	medición	variable/indicador	medición
Variable	(Dimension)	(Indicator)	(Values)	(Measurement criteria)	(Type of variable/indicator)	(Measurement instrument)
Immunogenicity of AD and SD vaccines among health care workers	Seroconversion (Clinical)	Comparison of HI [*] GMT [†] of serum collected at Day 28 (post- vaccination specimen) and at the end of the influenza season (end of season specimen) to serum collected at Day 0 (pre- vaccination specimen) for each vaccine (AD and SD)	Person seroconverted following vaccination Person did not seroconvert following vaccination	Post- vaccination/end of season HI GMT \geq 1:40 if pre-vaccination HI GMT <1:10 OR 4-fold rise in post- vaccination/end of season HI GMT if pre- vaccination HI GMT \geq 1:10 Post- vaccination/end of season HI GMT <1:40 if pre-vaccination HI GMT <1:10 OR <4-fold rise in post- vaccination/end of season HI GMT if pre- vaccination HI GMT \geq 1:10	Quantitative Continuous	Haemagglutination inhibition assay (laboratory)
	Seroprotection (Clinical)		Person is seroprotected following vaccination	Post- vaccination/end of season HI GMT ≥1:40	Quantitative Continuous	Haemagglutination inhibition assay
			Person is not seroprotected	Post- vaccination/end of season		

	following	HI GMT <1:40	
	vaccination		

*HI = haemagglutination inhibition

[†]GMT = geometric mean titer

Secondary Objective 5: To evaluate laboratory-confirmed influenza illness rates in the group receiving AD influenza vaccination compared to the group receiving SD influenza vaccination.

Variable	Dimensión	Indicador	Valores	Criterios de medición	Tipo de variable/indicador	Instrumento de medición
	(Dimension)	(Indicator)	(Values)	(Measurement criteria)	(Type of variable/indicator)	(Measurement instrument)

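### The end-of-season comparison counts influenza infection as seroconversion and its blood draw is dated two ways, so alone it cannot show how long the vaccine response lasts

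*Combined protocol and SAP*

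**What the plan says.** Section 7 sets the primary objective at two time points: "at approximately 28 days after vaccination and at the end of season, among HCP". Section 10.13 is narrower. It states that "The primary outcome to be measured will be seroconversion at day 28 after vaccination", and adds that "We will also measure HI GMT at the end of season".

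The variable table in section 11.1 applies one seroconversion rule to both later sera, each compared with Day 0: a titre of at least 1:40 if the baseline is below 1:10, otherwise a four-fold rise. A positive result at either time is labelled "Person seroconverted following vaccination". The text of 11.1 analyses every participant, and its summary table uses a per-protocol set defined as everyone vaccinated. PCR results from illness swabs are used for secondary objective 5 and are not linked to the primary serology. Section 11.2.2 lets locally circulating viruses determine the haemagglutination inhibition (HI) panel.

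The study timeline (section 3) puts the last blood sample at D180-200. Sections 2, 10.7 and 10.12 put it at the end of the season, which section 10.8.4 determines from surveillance. Enrolment is also described in two ways. Section 10.1 says "The participation from each subject will be from the enrollment (March approximately) until the end of the influenza season", and section 10.4 says "Enrollment will begin. during influenza season in Peru". Section 2 describes influenza in Peru as year-round with "increases during the months of June to October, which coincides with winter".

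**The concern.** A rise between Day 0 and the end of the season can come from the vaccine, from influenza infection, or from both. The rule credits all of it to vaccination. Infection adds responders to both arms, and adds more where fewer people had already responded and where more people are infected. If AD protects better, SD gains more infection-driven responders and the better vaccine looks less immunogenic. End-of-season seroprotection, defined only as a titre of at least 1:40, has the same problem.

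The draw date matters because it decides how much exposure and how much waning each serum reflects. Randomisation balances timing and exposure opportunity between arms, but it does not settle what is being measured. A narrowed difference at season end could be waning, infection or draw timing, and the planned analysis could not tell these apart.

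**Working it through.** The plan gives no attack rate, no seroconversion rate and no figure for this effect, so there is none of its own to reproduce. The check has two parts.

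**1. Infection counted as response.** All inputs here are assumptions:
- vaccine-only end-of-season seroconversion q of 35% (AD) and 27% (SD)
- 80% of infections with the tested strain produce a four-fold rise, independently of vaccine response
- AD prevents 30% of infections
- SD strain-specific attack rate a

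Observed rate = q + (1 − q) × attack rate × 0.8.
- AD: 0.35 + 0.65 × 0.7a × 0.8 = 0.35 + 0.364a
- SD: 0.27 + 0.73 × a × 0.8 = 0.27 + 0.584a
- Difference = 0.08 − 0.22a

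| SD attack rate | Observed difference (true 8.0 points) |
|---|---|
| 2% | 7.6 |
| 5% | 6.9 |
| 10% | 5.8 |
| 20% | 3.6 |

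Other assumptions give the following:
- If AD prevents no extra infection, the difference is 0.08 − (0.65 − 0.73) × (−0.8a) = 0.08 − 0.064a, which is 7.7 points at 5% and 6.7 at 20%.
- With 40% against 30% and AD halving infection, 10.0 points becomes 9.4, 8.4, 6.8 and 3.6 at attack rates of 2%, 5%, 10% and 20%.
- With no true difference (30% in both arms), AD halving infection and a 20% attack rate, AD is 0.30 + 0.70 × 0.10 × 0.8 = 35.6% and SD is 0.30 + 0.70 × 0.20 × 0.8 = 41.2%. SD looks 5.6 points better.
- With the seroprotection rates in section 10.2 (91% and 78%), there is less room for infection to add responders. At a 20% attack rate with AD halving infection, AD is 0.91 + 0.09 × 0.10 × 0.8 = 91.7% and SD is 0.78 + 0.22 × 0.20 × 0.8 = 81.5%. The 13.0 points become 10.2.

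**2. Dates in 2022.**
- Vaccination on 1 to 31 March: 1 March + 180 days = 28 August, and 31 March + 200 days = 17 October.
- If the season ends on 31 October, that is day 244 for someone vaccinated on 1 March and day 214 for 31 March. Both lie outside D180-200.
- If the season ends on 1 October, it is day 214 and day 184 respectively, so part of the March intake falls inside the window.
- The two definitions agree only for vaccination between 15 March and 4 April (season end 1 October) or between 14 April and 4 May (season end 31 October).
- For vaccination from 1 June, 31 October is day 152 or earlier, again outside the window.

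**The case against.** **Scope.** A reader might infer that half the primary endpoint is compromised. The documents do not support that: section 10.13 names only Day 28 seroconversion as the primary outcome. Following vaccination can also be read as a statement about time, and no objective uses the word persistence. The randomised comparison at season end remains a valid answer about response from any cause. This stands. But the end of the season is written into the primary objective, and section 2 says the three samples evaluate immune responses to vaccination, so the interpretation still needs a rule.

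**Size.** A reader might take the larger shrinkages as the expected bias. Every input is assumed. HI is read virus by virus, so the relevant attack rate is strain-specific: an overall 20% spread evenly over four vaccine strains would be 5% for each. The effect runs from trivial to serious, and the documents cannot place it.

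**Dates.** A reader might call the two dates incompatible, or conclude that sera would be drawn months after the season. Neither follows. Section 10.8 expects about 10 to 20 weeks of circulation. If it began on 1 June (an assumption), it would end between 10 August and 19 October, which overlaps D180-200 for a March intake. The reading of enrolment during the season rests on a visibly broken sentence in section 10.4, where a date may have been lost, while section 10.8 refers to pre-season illness reports after enrolment. The dates are unreconciled rather than irreconcilable.

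**Existing handling.** The ITTm1 and ITTm2 sets in section 11.1 are split by influenza after vaccination. They are assigned to secondary objectives 1 and 2, whose text defines the groups by 2016-2021 infection history. They do not repair the primary comparison.

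**Conclusion.** The point holds for the end-of-season comparison in the primary objective. As written, that comparison counts infection-driven rises as seroconversion following vaccination. It can be read as response at season end from any cause, but not, alone, as duration of vaccine response. If AD prevents more infection, the bias runs towards SD.

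The magnitude is unknown. Under the first set of assumptions an 8.0-point difference becomes 7.6 to 3.6 points over strain-specific attack rates of 2% to 20%. With low and equal attack rates the effect is negligible.

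The Day 28 primary outcome lies outside this point. If vaccination did take place during circulation, infection could also reach the Day 28 serum, which is a further reason to settle the enrolment date. The two dates for the last draw can coincide, but only for a vaccination window of about three weeks for any given season end.

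**What to change.** 1. Keep the all-participant end-of-season analysis and describe it as response from any cause.
2. Pre-specify, before unblinding, a supplementary analysis that uses Day 28 status, for example seroconversion at both Day 28 and season end, each against Day 0. A response that appears only after Day 28 is then not credited to the vaccine, and a participant who seroconverted by Day 28 and was later infected is not scored as a failure.
3. Report by arm the number with PCR-confirmed influenza of that type or subtype, or with a four-fold or greater rise from Day 28 to season end, split by Day 28 status. PCR alone is not enough, because swabs depend on reported symptoms and pre-season illness is not swabbed.
4. Base any statement on lasting response on both analyses.
5. Reconcile D180-200 with the surveillance-defined season end, and the two statements on enrolment timing. Report days from vaccination to draw by arm.

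A simpler rule that scores every infected participant as not seroconverted should be avoided, because it reverses the bias. Under the first set of assumptions, with all infections detected and a 20% attack rate, it gives 0.35 × 0.86 − 0.27 × 0.80 = 8.5 points instead of 8.0. With 30% in both arms it gives 0.30 × (0.86 − 0.80) = 1.8 points in favour of AD where there is no difference.

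The cost is SAP wording and one more analysis on sera and swabs already planned. A limitation remains: a Day 28 responder whose titre waned and was then boosted by infection still counts as a lasting response.

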Laboratory- confirmed influenza illness rates in HCP receiving AD	Clinical	Comparison of persons who did and did not become sick with influenza after receiving the AD or SD	Person became sick with influenza after receiving AD or SD vaccine Person did not become	Nasal swab specimen tests positive for influenza by PCR	Quantitative Discrete	PCR assay (laboratory)
vaccine		vaccine	sick with influenza after receiving AD or SD vaccine	Nasal swab specimen tests negative for influenza by PCR		

Secondary Objective 6: To assess the adverse events among HCP receiving SD and AD influenza vaccines

				Criterios de	Tipo de	Instrumento de
Variable	Dimensión	Indicador	Valores	medición	variable/indicador	medición
	(Dimension)	(Indicator)	(Values)	(Measurement criteria)	(Type of variable/indicator)	(Measurement instrument)
Adverse events in HCP receiving AD vs. SD vaccine	Anticipated (Clinical)	Local reactions: pain on vaccination site, swelling, lump itching, bruising	Yes	Person had a local and/or systemic reaction(s) after receiving AD or SD vaccine	Quantitative Discrete	Post-vaccination surveillance via follow-up visits and monitoring (calls, surveys)

	AND/OR Systemic reactions: fever (≥38°C), muscle ache, joint pain, headache, malaise, fatigue, weakness, sweating, shivering	No	Person did not have a local and/or systemic reaction(s) after receiving AD or SD vaccine		
	Death, life- threatening adverse event, hospitalization or prolongation of existing	Yes	Person had a serious adverse event after receiving the AD or SD vaccine		Post-vaccination surveillance via
Serious, Unanticipated (Clinical)	hospitalization, a persistent or significant incapacity affecting normal life activities, and other unanticipated event that seriously impacts the health of participants	No	Person did not have a serious adverse event after receiving the AD or SD vaccine	Quantitative Discrete	follow-up visits, monitoring (calls, surveys), and hospitalizations

Below we describe the statistical tests that we will perform to address each primary and secondary objective, highlighting which study population will be included for each analysis. All statistical tests will be performed with a significance level of 5% and a statistical power of 80%.

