Primary objective: To determine if AD influenza vaccine generates superior immunogenicity than the nonadjuvanted SD influenza vaccine, at approximately 28 days after vaccination and at the end of season, among HCP. We will use Wilcoxon signed-rank tests to assess HI GMT differences and differences in proportions of HCP who seroconverted and were seroprotected between AD and SD vaccination groups. All HCP included in the clinical trial will be included as the study population for these analyses.

Secondary objectives:

1) To compare immune responses post-vaccination, at approximately 28 days after vaccination and at the end of season, among HCP with a history of PCR-confirmed influenza infection during any of the six cohort years (2016 to 2021). The outcome variables will be the same as those of the primary objective matrix of variables, but dividing the enrolled study population to include only the HCP with a history of PCR-confirmed influenza infection during any of the six-year cohort (2016-2021). We will use Wilcoxon signed-rank tests to assess HI GMT differences and differences in proportions of HCP who seroconverted and were seroprotected between AD and SD vaccination groups. Only HCP in the clinical trial with a history of PCR-confirmed influenza infection during any of the six cohort years (2016 to 2021) will be included as the study population for these analyses.

2) To compare immune responses post-vaccination, at approximately 28 days after vaccination and at the end of season, among HCP with no history of PCR-confirmed influenza infection during the six cohort years (2016 to 2021), among those with data available for the six cohort years. The outcome variables will be the same as those of the matrix of variables in the primary objective, but dividing the enrolled study population to include only the HCP with no history of PCR-confirmed influenza infection during any of the six-year cohort (2016-2021). We will use Wilcoxon signed-rank tests to assess HI GMT differences and differences in proportions of HCP who seroconverted and were seroprotected between AD and SD vaccination groups. Only HCP in the clinical trial with no history of PCR-confirmed influenza infection during any of the six cohort years (2016 to 2021) will be included as the study population for these analyses.

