5) To evaluate laboratory-confirmed influenza illness rates in the group receiving AD influenza vaccination compared to the group receiving SD influenza vaccination. Using data collected through active surveillance, we will calculate incidence densities and use descriptive statistics and Z-test to assess differences in the proportion of HCPs who had laboratory-confirmed influenza (as determined by PCR on nasal swab samples) during the period of the clinical trial among the HCP who received the influenza vaccines AD vs. SD. A Cox regression model will be used to adjust the risk of developing influenza between both groups according to demographic and occupational characteristics. Health personnel participating in the clinical trial will be included as a study population for these analyzes.

6) To assess the adverse events among HCP receiving SD and AD influenza vaccines. Using data collected through active surveillance, we will use descriptive statistics and the Z test to assess the differences in the proportions of adverse events (anticipated and serious) between the HCP who received the AD and SD

influenza vaccines. All health personnel participating in the clinical trial will be included as a study population for these analyzes.

Table 1: Summary of Analysis by Endpoints and Analysis Populations.

OBJECTIVE	VALUATION CRITERIA	STATISTICAL TEST	POPULATION OF ANALYSIS
Primary Efficacy Analysis			
To determine if the AD influenza vaccine generates superior immunogenicity than the vaccine against SD influence without adjuvant among the HCP.	Immunogenicity - superior serumconversion of AD vaccine versus SD vaccine in HCP.	Wilcoxon signed rank test.	PP population
Secondary Efficacy Analysis			
To compare the post-vaccine immune response, in approximately 28 days after vaccination and at the end of the influenza season, among the HCP with a history of influenza infection confirmed by PCR result during any of the 6 years during the previous cohort study (2016 to 2021).	Post-vaccination immune responses, approximately 28 days after vaccination and at the end of the season, among HCPs with a history of PCR-confirmed influenza infection	Wilcoxon signed rank test.	ITTm1

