11.2.2 Serology analysis

Samples will be processed and then frozen at -20°C. Specimens will be stored at the local CDC-approved local laboratory for serologic testing and then will be shipped to the US CDC laboratory for serologic testing at the end of the study. Hemagglutination inhibition (HI) assay will be run in duplicate using a CDC-approved protocol. Standard procedures typically include preparing a turkey (for A/H1N1 and influenza Bs) or guinea pig red blood cells (RBC) (for A/H3N2) suspension and treating serum samples with receptor-destroying enzyme to remove nonspecific inhibitors. Nonspecific agglutinins are removed by serum adsorption with packed RBCs. Serum is diluted 2-fold starting from 1:10. The HI titer is the reciprocal of the serum dilution in the last well with complete hemagglutination inhibition.

The panel of influenza viruses to be included in the HI assay will be determined depending on locally circulating viruses during enrollment and historically, including viruses in circulation during the previous 2-6 years.

Samples will be also shipped to US CDC labs for additional testing with additional immunological assays for influenza and other respiratory pathogens (e.g. RSV, parainfluenza viruses, human metapneumovirus, adenoviruses, and coronaviruses) or other agents that cause respiratory diseases such as bacteria, as well as for the biorepository.

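### The plan does not define one primary superiority comparison: measure, time, strain and success rule are left open or stated differently, and every test is run at 5%

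*Combined protocol and SAP*

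**What the plan says.** The places that bear on the primary comparison do not agree.

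- **Section 10.13 (Study outcomes):** "The primary outcome to be measured will be seroconversion at day 28 after vaccination". It then adds "We will also measure HI GMT at the end of season" and defines seroprotection, without calling either one primary.
- **Section 7 (primary objective):** the aim is to show "superior immunogenicity than the non-adjuvanted SD influenza vaccine, at approximately 28 days after vaccination and at the end of season, among HCP". This covers two times and names no measure.
- **Section 11.1, variable table for the primary objective:** lists seroconversion and also seroprotection ("Person is seroprotected following vaccination"), each at Day 28 and at end of season.
- **Section 11.1, analysis text for the primary objective:** "We will use Wilcoxon signed-rank tests to assess HI GMT differences and differences in proportions of HCP who seroconverted and were seroprotected". The three measures are not ranked.
- **Section 11.1, summary table of analyses, primary row:** "Immunogenicity - superior serumconversion of AD vaccine versus SD vaccine in HCP". No time is given.
- **Sections 2 and 8 (summary, justification):** the stated aim is superior seroprotection.
- **Section 10.2 (sample size):** Table 1 is built on seroprotection for A(H1N1p), 91% against 78%, and has no information for A(H3N2) or B. Table 2 varies the seroprotection rate.

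On strains, section 12 lists four in each vaccine. Section 11.2.2 leaves the assay panel open: "The panel of influenza viruses to be included in the HI assay will be determined depending on locally circulating viruses during enrollment and historically". On error rates, section 11.1 says "All statistical tests will be performed with a significance level of 5% and a statistical power of 80" per cent. No section names a primary strain, says how many strains must succeed, or gives a testing order or adjustment.

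**The concern.** HI seroconversion is determined separately for each virus, so even if section 10.13 is taken as decisive, the primary outcome produces several results, one per antigen. Without a written rule, AD could be called superior because one strain succeeded, because a particular strain succeeded, or because all did. These rules have different error rates and mean different things. The broader primary objective adds further candidates. If the rule is settled only after the results are known, the false-claim rate is not controlled at any stated level. The trial is meant to inform health authorities about vaccinating health care personnel, so what counts as success should be readable from the plan.

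**Working it through.** **Inputs.**
- 5% per test: section 11.1.
- Two-sided testing: section 10.2, for the sample size only; section 11.1 gives no side. Two-sided 5% is 2.5% in AD's favour, critical value 1.960.
- Four strains: section 12.
- 91% and 78% seroprotection, 20% loss: section 10.2.
- 400 per arm: sections 10.2 and 10.4.
- Correlations between strains, and any seroconversion rate: not in the documents, so assumed below.

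**Step 1. The plan's own figure.** With the unpooled formula, n = (1.960 + 0.842)² × (0.91×0.09 + 0.78×0.22) / 0.13² = 7.849 × 0.2535 / 0.0169 = 117.7, so 118 per group; 118 × 1.2 = 141.6, so 142. Both match Table 1. The sizing is thus for one comparison, of one strain, on seroprotection, at two-sided 5%, with no allowance for several strains.

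**Step 2. Illustration: any one of k strains may carry the claim.** Assume no true difference in any strain, valid two-sample tests, and k test statistics with equal correlation ρ. For independent statistics the chance of at least one false claim for AD is 1 − 0.975^k; for k = 4 this is 1 − 0.9037 = 9.6%. For ρ > 0 it is 1 − ∫ φ(x) Φ((1.960 − √ρ·x)/√(1−ρ))^k dx, evaluated numerically:

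| ρ (assumed) | 0 | 0.3 | 0.6 | 0.8 | 0.9 |
|---|---|---|---|---|---|
| any of 4 | 9.6% | 8.7% | 7.2% | 5.7% | 4.7% |
| any of 6 (a larger panel, assumed) | 14.1% | 12.2% | 9.3% | 6.9% | 5.4% |
| all 4 must succeed | <0.1% | <0.1% | 0.2% | 0.5% | 0.9% |

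A single strain named in advance gives 2.5%. The all-strain rule stays at or below 2.5% even if AD truly is better for some strains.

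**Step 3. Power cost of Holm.** Holm's strictest step for four strains uses 0.05/4 = 0.0125 two-sided, critical value 2.498. Power = Φ((d − z·s0)/s1), where d is the difference, s0 = √(2p̄(1−p̄)/n) and s1 = √((p1q1 + p2q2)/n).

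- *Seroprotection, 78% vs 86%* (a 10% relative increase on 78% is 85.8%), n = 400: s0 = 0.02717, s1 = 0.02702. At 5%: (0.08 − 0.05325)/0.02702 = 0.99, power 84%. At 1.25%: (0.08 − 0.06786)/0.02702 = 0.45, power 67%.
- *Seroconversion, 57% vs 65%* (assumed, same 8-point gap), n = 400: s0 = 0.03449, s1 = 0.03437. At 5%: (0.08 − 0.06760)/0.03437 = 0.36, power 64%. At 1.25%: (0.08 − 0.08615)/0.03437 = −0.18, power 43%.
- With 20% loss (400 × 0.8 = 320 per arm), the falls are 75% to 55% and 55% to 34%.

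**The case against.** Four points can be made for the plan.

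*Section 10.13 already names one outcome at one time.* This is largely fair. The summary table agrees on the measure and lacks only the time, and no section calls seroprotection, GMT or end of season a primary outcome. But sections 7 and 11.1 place them under the primary superiority objective without ranking, the stated aim and the sizing use seroprotection, and section 10.13 says nothing about strain.

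*A(H1N1)pdm09 is implicitly the primary strain.* Section 10.2 uses it for sizing only, for a different measure, and marks the other viruses as lacking information. That points to available data, not to a designated strain.

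*Strain-by-strain claims each keep their own 2.5%.* True, and a plan may choose that. It would have to say so, and limit its conclusion to the strain concerned; the hypothesis here is stated for the vaccine as a whole.

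*The inflation figure is hypothetical.* This stands. A reader might infer that the trial runs a 6–10% false-claim risk. The documents do not support that: no section states an any-one-strain rule, the panel size is open, the correlations are assumed, and the signed-rank test named in section 11.1 is not the two-sample test assumed here (a separate matter). A reader might also count 3 measures × 2 times × 4 strains = 24 tests and quote 1 − 0.975^24 = 46%. That treats strongly related results as independent and counts as primary what section 10.13 does not. Nor does anything show an intention to choose the rule after seeing results.

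**Conclusion.** The point holds as under-specification with a real internal conflict. The primary measure and time differ between sections, and strain, number of strains required and multiplicity procedure are absent, while a blanket 5% applies to every test. Read as written, superiority could be rested on any of several unadjusted tests. The actual false-claim rate cannot be calculated from the documents. It is at or below 2.5% under a single named strain or an all-strain rule. Under an any-one-of-four rule it would be between 4.7% and 9.6% for assumed correlations from 0.9 to 0, and higher with a larger panel. These figures take two-sided tests and no true difference in any strain. The plan should be amended; the correction needs no new data.

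**What to change.** Before unblinding:

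1. **One primary outcome.** Make Day-28 seroconversion the single primary outcome in section 7 and throughout section 11.1 (variable table, analysis text, and the primary row of the summary table, with the time added). Move end of season, seroprotection and GMT to secondary, reported with estimates and 95% confidence intervals. Reconcile the seroprotection aim in sections 2 and 8 with this, and state in section 10.2 that the sizing rests on seroprotection rates.
2. **Fixed antigens.** List the primary HI antigens in section 11.2.2, for example the four vaccine strains. Section 12 gives different A(H3N2) strain names for the two products; these entries must be reconciled first.
3. **One testing procedure.** Replace the blanket 5% for the primary comparison with a stated rule. One option is Holm over the four strains at an overall two-sided 5%, claiming superiority only for strains that pass. Another is a fixed order starting with A(H1N1)pdm09. The choice is the sponsor's; what matters is that it is written down.

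**Cost.** A protocol amendment and revised analysis text, and fewer confirmatory claims. At Holm's strictest step with 400 per arm, power falls from 84% to 67% on the seroprotection rates of 78% vs 86%. For seroconversion the documents give no rates, so the loss is unknown; the assumed 57% vs 65% gives 64% falling to 43%. A fixed order costs no power for its first strain, but no later strain can be claimed if that one misses.
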